## **A. STUDY PROCEDURES FOR PARTICIPANT DISTRESS, IN-CLINIC OR VIA TELEPHONE**

1. **MILD TO MODERATE DISTRESS (NO THOUGHTS OR INTENT OF HARM TO SELF OR OTHERS)**
  - a. During the in-clinic visits or via telephone, if the participant reports mild to moderate stress (but no suicidal thoughts or morbid ideations such as thoughts of wanting to be dead), the participant will be asked to make an appointment with primary obstetric provider or primary care provider. The patient will also be provided a listing of community resources and encouraged to seek help.
  - b. Counselor will help the participant develop an action plan to be seen by a mental health professional should their distress persist over multiple sessions or worsen.
  - c. Counselor will document the conversation and support materials provided.
  - d. Continued distress without professional assistance and support can be a reason to temporarily or permanently withdraw the participant from the **GWG** or **PPWL** Intervention protocol. Due to safety concerns, notification of withdrawal from the study based on continued distress will result in formal notification of the participant’s command.

2. **SEVERE DISTRESS AND THOUGHTS OR INTENT OF HARM TO SELF OR OTHERS WITH NO INTENT OR PLAN** Participant reports suicidal thoughts or thoughts of harming others but no intent or plan.
  - a. Counselor will develop an action plan to get help from a mental health professional. This conversation with the participant and the action plan will be documented.
  - b. Counselor will follow-up in two business days to ensure that the participant has an appointment with mental health scheduled.
  - c. Counselor will also inform the participant that if their condition worsens the following emergency resources are available:
    - 1) Mental Health Clinic in WHASC (open for Walk-Ins during duty hours: [contact])
    - 2) SAMMC Emergency Department: [contact]
    - 3) Crisis Hotline call: [name]
  
3. **SEVERE DISTRESS AND PLANS OR CLEAR INTENT TO HARM SELF OR OTHERS**
  - a. Participant reports suicidal thoughts or thoughts of harming others and intent or plan.
  - b. Once a participant endorses suicidal intent the counselor will attempt to keep them on the phone.
  - c. Whether the Counselor – Participant contact is by phone or in-person, the Counselor will attempt to maintain contact with the participant, identify the location of the Participant and maintain verbal contact until help arrives.
  - d. Counselor will contact another staff member and indicate they have an emergency and direct them to call the appropriate emergency number (911; Lackland Command Post: [contact]; Security Forces: [contact]; Ambulance: [contact]; SAMMC Police Duty Officer [contact]) and provide an address.
  - e. Counselor will document the conversation with the prospective participant and all actions taken.

## **B. DOCUMENTATION OF ADVERSE EVENTS**

1. Incidences of EPDS scores greater than or equal to 10 may be documented as adverse events.
2. In the event of an adverse event, the participant should be followed to resolution of the event, or to its stabilization.

### **4.9.1. Minimizing Risks:**

This study follows evidence-based lifestyle recommendations for weight management and improving health, including diet change and regular exercise. If followed according to program guidelines, no adverse medical conditions are expected to result from the research activities.

There are no major risks associated with taking measurements (i.e. height, weight, and waist circumference), taking a health history or collecting questionnaire data. There is, however, the potential risk of loss of confidentiality. Every effort will be made to keep participant information confidential as described in Section 4.8. In the event that questions asked make participants feel uncomfortable, they may refuse to answer and may take a break at any time during a study visit. However, we are not collecting any information that would in any way jeopardize participants' careers

Any significant new findings developed during the course of this research project, which may impact upon the safety and efficacy of the procedure or treatment under study and consequently influence participants' willingness to continue participation, will be provided to them.

#### **4.9.2. Vulnerable Populations: Pregnant women**

#### **4.9.3. Clinical Care:**

As all participants will be female active duty military members and DoD TRICARE beneficiaries, medical care (if needed) is provided at no cost through their Military Treatment Facility (MTF).

#### **4.9.4. Injury Compensation: N/A**

#### **4.9.5. Data Safety Monitoring:**

The trial will be conducted in compliance with this protocol, International Conference on Harmonization (ICH) Guidelines for Good Clinical Practice (GCP), and any applicable national and international regulatory requirements. The principal and associate investigators will be monitoring all aspects of the study in accordance with the appropriate regulations in order to:

- 1) Ensure protection of study subjects, compliance with the protocol, and accuracy and completeness of records.
- 2) Verify the prompt reporting of all data points, including reporting Serious Adverse Events (SAEs) and checking availability of signed informed consent,

Note: A Data Safety Monitoring Plan (DSMP) will be developed for this study and the Data Safety Monitoring Board (DSMB) will meet yearly to review participant safety.

#### **5.0. Alternatives:**

Alternatives include not participating in the study, consulting with their Primary Care Provider (PCP) or OB clinician to assist them with weight management efforts, or self-monitoring of dietary intake and physical activity to achieve weight management during pregnancy and postpartum. Meal replacements may also be bought at local stores.

#### **6.0. Data Analysis:**

We will analyze changes in weight and abdominal circumference, as well as data based on other measures from baseline, gestational Week 32 and Week 36, as well as at 6-weeks, 6-months, and 12-months postpartum.

#### **6.1. Outcome Measures:**

The primary study outcomes will be a comparison of GWG from baseline to the final gestational weight (either week 32 or week 36, depending on the delivery date) as well as a comparison of weight loss from 6-week postpartum to 12-months postpartum for the 3 intervention arms.

#### **6.2. Sample size estimation/power analysis:**

The study aims to enroll 755 (with the intent for 450 subjects completing the study) participants, 150 participants in each group. This distribution will provide a diverse representation within each intervention group and will provide the necessary information for data and power analysis.

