**3.0. Research Plan:**

**3.1. Purpose:**

- 1) To randomize 450 participants to 1 of 3 arms: a) a gestational weight gain intervention (GWG-only); b) a postpartum weight loss intervention (PPWL-only), or c) a combined gestational weight gain and postpartum weight loss intervention (GWG+PPWL), and to determine the efficacy of the interventions on GWG as well as PPWL;
- 2) To identify the impact of the interventions on pregnancy-related medical outcomes and health care utilization (from the electronic medical record) and fitness test data (pregravid to 12-month postpartum, from the military fitness database);
- 3) To determine the impact of treatment engagement process data (e.g., session participation, self-monitoring, meal replacement adherence) on intervention outcome.

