#### **7. Number of Subjects:**

TOTAL NUMBER OF SUBJECTS (nation-wide/study-wide): WHASC and SAMMC – 755 with 450 completing the study

**8. Use of an Investigational New Drug:** N/A

**9. Use of an Investigational Device:** N/A

**10. Use of a Placebo:** N/A

**PROTOCOL FOR CLINICAL INVESTIGATION – NON-EXEMPT HUMAN  
(Wilford Hall Ambulatory Surgical Center – WHASC)**

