### 3.6. Research Design and Methods:

We will implement a stepped-care GWG intervention and a PPWL intervention for women with TRICARE benefits, while accommodating the unique military lifestyle and environment. We will randomize 450 participants to 1 of 3 arms: a) a gestational weight gain intervention (GWG-only); b) a postpartum weight loss intervention (PPWL-only), or c) a combined gestational weight gain and postpartum weight loss intervention (GWG+PPWL) in order to determine the efficacy of the interventions on GWG as well as PPWL. This design will allow the PPWL-only arm to be the comparison group for GWG (at the final pregnancy follow-up visit); the GWG-only arm to be the comparison group for PPWL (at 6-months and 12-months follow-up) and the GWG+PPWL arm to determine the additive or synergistic effects. Study measures will be obtained at screening, baseline, gestational week 32 and 36, and 6-weeks, 6-months, and 12-months postpartum and will include weight, height, maternal and infant medical outcomes, health care utilization, fitness test scores, waist circumference, self-reported exercise behaviors and nausea symptoms, accelerometry, feeding practices, demographics and program satisfaction. Process measures (e.g., session participation, self-monitoring) will be collected throughout the trial.

No inducements, monetary or otherwise, will be offered to terminate a pregnancy. Individuals engaged in the research will have no part in any decisions as to the timing, method, or procedures used to terminate a pregnancy and individuals engaged in the research will have no part in determining the viability of a neonate (45 CFR 46.204).

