#### 3.6.1. Interventions, Observations, or Data Sought:

**Procedure:** Interested individuals will be directed from our recruitment materials (e.g., posters, flyers, business cards, listservs, and electronic media) to visit the study recruitment office (located in the obstetric clinics) to learn more and determine whether they meet the eligibility criteria. If, after learning more about the study, individuals continue to be interested, written informed consent will be obtained and measures will be administered. The potential participant will also be asked to complete a one-week dietary and exercise self-monitoring run-in, turn in a copy of their fitness scores to study staff (if active duty), and receive medical clearance from their obstetrician to participate. (Note: In the unfortunate event that a potential participant miscarries before being randomized, she will have the opportunity to re-screen if she chooses.) Should she continue to be interested, she will return for a Baseline Visit and will be randomized to 1 of 3 conditions: a) GWG-only; b) PPWL-only; or c) GWG+PPWL and oriented to the assigned treatment condition.

**Randomization:** Participants (n=450) will be randomly allocated to 1 of the 3 conditions, using a computer algorithm under the direction of the study biostatistician, [name], with a sequence blocked by screening BMI category (i.e., normal weight, overweight, obese) in order to ensure equal distribution by condition with respect to BMI category. Each condition will have the same number of subjects.

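### 450 is given both as the number randomized and as the number completing; on the natural reading both hold only if nobody is lost after randomization.

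*Combined protocol and SAP*

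**What the plan says.** **450 as the number randomized.** This appears in four places in the combined protocol and SAP:
- Section 3.1 (Purpose), in both the front summary and the main protocol: "To randomize 450 participants to 1 of 3 arms".
- Section 3.6: "We will randomize 450 participants to 1 of 3 arms".
- Section 3.6.1, Randomization: "Participants (n=450) will be randomly allocated to 1 of the 3 conditions", followed by "Each condition will have the same number of subjects".

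**450 as the number completing.** This appears in three places:
- Section 7 of the front summary: "755 with 450 completing the study".
- Section 6.2: "The study aims to enroll 755 (with the intent for 450 subjects completing the study) participants, 150 participants in each group".
- The table in section 6.4, which sets 755 enrolled against 450 completing and attaches the words *full study* to both numbers.

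**Order of events.** In section 3.6.1, Procedure, "written informed consent will be obtained and measures will be administered" comes first. The one-week run-in and obstetric clearance follow, and only then "she will return for a Baseline Visit and will be randomized to 1 of 3 conditions".

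**Follow-up.** Section 3.6.2 schedules the last visit at 12 months postpartum, section 6.1 makes weight at that visit part of a primary outcome, and section 3.6.4 gives 21 months of participation from enrollment. No section defines *enrolled* or *completing*, gives a loss rate, or divides losses into those before and those after randomization.

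**The concern.** One number is doing two jobs. Sections 3.1, 3.6 and 3.6.1 put 450 at the start of the randomized comparison. Sections 6.2, 6.4 and 7 (front summary) put it at the end of the study. With follow-up from early pregnancy to a year after birth, those two counts would normally differ.

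What is at stake is the stated size of the trial at the 12-month comparison, on which Hypothesis 2 rests. The only per-group figure written out, 150, stands in section 6.2 in the same sentence as both the enrolled and the completing totals. A reader can work out the starting size from section 3.6.1 but cannot tell what size the sponsor expects at 12 months. If 450 randomized is correct, the completing size given in three places is missed as soon as one participant is lost.

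**Working it through.** **1. Reproducing the stated figures.** 450 / 3 = 150 per group, so the per-group figure agrees with the total. The 755 cannot be rebuilt, because the plan gives no loss rate. The implied overall loss is 755 - 450 = 305, and 305 / 755 = 40.4%.

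**2. What completing most naturally means.** Section 6.4 refers to the full study, and the last scheduled visit is at 12 months postpartum. The 21 months in section 3.6.4 is long enough to reach it. Assuming delivery at 40 weeks:
- enrollment at 12 weeks of gestation gives 28 weeks + 12 months = 18.4 months;
- enrollment at 4 weeks gives 36 weeks + 12 months = 20.3 months.

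**3. When the two uses of 450 agree.** Let d be the proportion lost after randomization. Completers = 450 x (1 - d). This equals 450 only at d = 0. All 305 losses would then fall between enrollment and randomization, and none in the months after it.

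**4. Whether the plan assumes d = 0 at 12 months.** It does not. Section 3.6.2 offers incentives to secure retention at every follow-up visit. Section 3.6.8 does promise a final gestational weight on every participant, but that sentence deals with early delivery and the prenatal outcome, not the 12-month visit.

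**5. What the 755 could be.**
- *Number consented.* The sequence in section 3.6.1 supports this, since consent precedes run-in, clearance and randomization.
- *Number entering the trial proper.* The label in the section 6.4 table points this way. If all 755 were randomized, however, that contradicts n = 450, and 755 / 3 = 251.67 is not a whole number, so exactly equal arms would be impossible.

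The text does not settle which is meant.

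**6. Size of the discrepancy.** The loss rates below are assumptions, since the plan gives none.

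| Assumed loss after randomization | Completing if 450 are randomized | Per arm |
|---|---|---|
| 0% | 450 | 150 |
| 10% | 450 x 0.9 = 405 | 135 |
| 20% | 450 x 0.8 = 360 | 120 |
| 30% | 450 x 0.7 = 315 | 105 |

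In the other direction, 150 completing per arm at 10%, 20% or 30% loss needs 150/0.9, 150/0.8 or 150/0.7. Rounded up, these are 167, 188 or 215 per arm, or 501, 564 or 645 in total.

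**The case against.** The best defence is that 755 are consented, 450 are randomized, and completing means getting through run-in and clearance. The figures would then agree. This cannot be excluded while the terms are undefined, but it fits poorly with the reference to the full study in section 6.4. Even if it is what the sponsor meant, the number expected at 12 months would then be missing from the plan.

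Other points on that side stand:
- The starting size is not in doubt: section 3.6.1 fixes 450 in equal arms, so 150 each. Only the 12-month size is unclear.
- Section 6.2 speaks of an aim and an intent, so these are targets, not guarantees. A target should still be one that the design can meet.
- The distress procedures under section 4.9 mention withdrawal from the study, but chiefly concern withdrawal from the intervention. They are weak evidence of expected loss of outcome data.
- Completing is not the same as being analysed. Section 6.3 is intention-to-treat, and section 3.6.2 allows scale uploads from participants who move away. The number with a 12-month weight may therefore exceed the number completing every visit.

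A reader might go further and infer that the trial is underpowered. The documents do not support that. They state no effect size, standard deviation, alpha, power or loss rate, so there is no power claim for attrition to undermine. The absence of a power calculation is a separate matter.

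**Conclusion.** The inconsistency is real. The plan uses 450 for the number randomized in four places and for the number completing in three. On the natural reading of completing, both are true only with no loss after randomization, which nothing in the plan assumes for the 12-month visit. The 755 is also ambiguous between the number consented and the number entering the trial.

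The conclusion depends on completing meaning 12-month follow-up; the wording mismatch and the undefined terms do not. The size of any shortfall depends on a loss rate that the plan does not give: 45, 90 or 135 below 450 at an assumed 10%, 20% or 30%. A reader might infer that more participants must be randomized. That follows only if 450 completers is the true target, which the documents leave open. The point is one of reconciling and restating sizes, and it should be fixed.

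**What to change.** Define *enrolled* and *completing*, and have the sponsor confirm what the 755 counts. Then, in sections 3.1 and 7 of the front summary and sections 3.1, 3.6, 3.6.1, 6.2 and 6.4 of the main protocol, state separately and in identical terms:
1. the number consented;
2. the number randomized, in total and per arm;
3. the number expected to have a 12-month postpartum weight, with the assumed loss after randomization.

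**If 450 randomized is confirmed,** restate the completing figure in section 7 (front summary) and sections 6.2 and 6.4 as below 450, and below 150 per group. This needs no extra participants. The only cost is a less favourable stated completing size.

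**If 450 completers is the target,** the randomized figure in sections 3.1, 3.6 and 3.6.1 is wrong and the sponsor must reconcile it. That would change the size of the trial: the illustrative totals above are 51, 114 or 195 more than the 450 stated. Whether 755 enrolled would be enough depends on the loss before randomization, which the plan would also have to state.

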#### **6.3. Statistical Analysis:**

All of the analyses will be performed with SASv9.4. Data will be examined for distributional normality and outliers prior to any analyses. Descriptive statistics will be generated for all variables of interest included in the analysis, overall and by treatment arm. Univariate comparisons will consist of t-test, chi-square test, ANOVA, and their respective non-parametric counterparts if needed, for continuous/categorical variables respectively. Primary analyses will be intention-to-treat, without regard to intervention adherence. We will use multivariable linear ANCOVA-like regression models for continuous outcomes, to model and compare

the GWG (Hypothesis 1) and PPWL (Hypothesis 2), in the 3 arms. Using these models, treatment effects will be estimated and tested by comparing change in group-specific means at the final prenatal visit and 12-months postpartum conservatively adjusting for baseline differences (which will be minimal by virtue of randomization) and in the case of hypothesis 2 for 6-weeks postpartum weight differences. Randomization validity will be assessed by comparing arms on baseline measures using chi-square tests, ANOVAs and other appropriate tests. If imbalances are found, we will consider adjusting the between-group analyses for potential confounders.

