**Intervention Overview:** The novel stepped-care behavioral GWG and/or PPWL intervention--designed to assist participants meet the Institute of Medicine (IOM)-recommended GWG guidelines and produce PPWL--will be based on the Look AHEAD Intensive Lifestyle Intervention. The Look AHEAD Intensive Lifestyle Intervention methods are consistent with those utilized in previous studies of effective approaches to producing appropriate GWG and PPWL. However, the Look AHEAD approach offers greater structure and support than some of the methods used in previous work. We will also tailor our intervention to the military lifestyle (e.g., managing stressors such as increases in dietary intake, reduced physical activity related to spouse deployment, environmental facilitators such as access to the free fitness centers). We have previously tailored our interventions to the military lifestyle and environment, and our programs have been extremely well received by military personnel.

**GWG Intervention:** The GWG intervention will begin upon randomization to the GWG-only or the GWG+PPWL arm, and continue until the birth of the participant’s child. This intervention will provide individual, telephone-based sessions (20-30 minutes each), as detailed in Table 1, by trained interventionists. The number of possible telephone sessions will depend on the gestational age at randomization and the level of support needed by the participant to meet the IOM guidelines. The intervention will focus on self-monitoring, clear goals (i.e., GWG, caloric intake exercise), and problem solving.

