**PPWL Intervention:** The PPWL intervention will begin at 6-weeks postpartum (when most women will be approved for weight loss and exercise by their obstetrician) for those participants randomized to the PPWL-only or the GWG+PPWL arms, and will continue until 12-months postpartum. The PPWL intervention will provide at least monthly individual, telephone-based sessions (20-30 minutes each), as detailed in Table 2, by trained interventionists. (The number of possible telephone sessions will depend on the level of support needed by each participant to meet her weight loss goals). Similar to the GWG intervention, the PPWL intervention will focus on self-monitoring; weight, dietary intake and exercise goals; and problem solving.

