### 3.6.8. Instrumentation:

- Contact information
- Demographics: Participants will complete a questionnaire regarding their age, parity, race, and ethnicity.
- Physical Assessment:
  - Weight: At all measurement visits, weight will be recorded in kilograms. Weight will be measured on a calibrated digital scale in duplicate, with the participant wearing light clothing and no shoes. While we will obtain the mother's weight at baseline, we will also obtain self-reported pregravid weight (before the last menstrual period). The difficulty of anticipating when a final weight should be obtained to capture the fullest extent of GWG was considered, and we elected to use an approach that afforded two possible weights that would be available for analytic purposes. The Week 36 weight will be the primary outcome except for mothers who deliver prior to 36 weeks, in which case we will use the Week 32 weight. Thus, we will have a final observation of GWG for all participants, regardless of whether they deliver earlier than 36 weeks.
  - Waist Circumference: As an indicator of subcutaneous and visceral abdominal fat, waist circumference will be measured (recorded in centimeters) using a non-distensible measuring tape and standard protocols for positioning.
  - Height: Height, using a wall-mounted stadiometer, will be recorded in centimeters. BMI will be calculated from measured weight and height.
- Physical Activity: We will assess physical activity, subjectively, using the International Physical Activity Questionnaire, as it has been used in other studies of gestational/postpartum weight management, has been validated against accelerometry, and has good test-retest reliability. We will also assess physical

activity objectively using the Actical accelerometer. Participants will be asked to wear the accelerometer for 7 days, including 2 weekend days and 3 weekdays.

- Weight Gain Recommendations: We will assess knowledge of weight gain recommendations at the Baseline visit, before randomization. One previous study has shown the gestational weight gain expectations, in a civilian population, predicted actual pregnancy weight gain; however, it is not certain whether this finding will replicate in a military population.

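### Section 6.3 names no contrast for Hypothesis 1, although the two GWG arms receive the same treatment until after the GWG endpoint; one combined contrast should be specified

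*Combined protocol and SAP*

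**What the plan says.** Section 3.2 states Hypothesis 1 as a claim that both arms receiving the gestational intervention will gain less than PPWL-only. Section 3.6 confirms the comparator: "This design will allow the PPWL-only arm to be the comparison group for GWG (at the final pregnancy follow-up visit". The arms, the direction and the control are therefore settled.

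The form of the test is not. Section 6.1 describes the primary outcomes as comparisons "for the 3 intervention arms". Section 6.3 is the only analysis text. It says ANCOVA-like models will compare "the GWG (Hypothesis 1) and PPWL (Hypothesis 2), in the 3 arms" and that "treatment effects will be estimated and tested by comparing change in group-specific means at the final prenatal visit and 12-months postpartum". It names no contrast, success rule, alpha or multiplicity rule, and section 6.2 adds none.

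The timing of treatment and endpoint matters here:

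- Section 3.6.1, GWG Intervention: "The GWG intervention will begin upon randomization to the GWG-only or the GWG+PPWL arm", and it runs until birth.
- Section 3.6.1, PPWL Intervention: "The PPWL intervention will begin at 6-weeks postpartum".
- Section 3.6.8, Weight: "The Week 36 weight will be the primary outcome except for mothers who deliver prior to 36 weeks", in which case the Week 32 weight is used.

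**The concern.** Up to the GWG endpoint, no assigned treatment component distinguishes GWG-only from GWG+PPWL. Section 6.3 nevertheless leaves at least three tests open: two arm-by-arm comparisons with PPWL-only (the natural reading, but not the only one), a 2-df test of three means, or one combined contrast.

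A three-arm model loses no precision in itself; any loss comes from the contrast taken from it. Each arm-by-arm test uses only half of the GWG-treated women. A 2-df test spends a degree of freedom on a difference between the two GWG arms that the prenatal treatment does not create. Under arm-by-arm testing the success rule also matters: accepting either result without adjustment raises the false-positive rate, and requiring both lowers power. These two harms are alternatives and do not add up. If the two tests disagree, the plan cannot say whether Hypothesis 1 is supported, and the choice could then be made after the data are seen. GWG is one of the two primary outcomes.

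**Working it through.** **Inputs from the documents.** Three arms of equal size (section 3.6.1, Randomization). Section 6.2 gives 755 enrolled, 450 completing and 150 per group. It gives no alpha, power, SD or effect size, so the sample size cannot be reproduced and there is no planned power figure to check against.

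**Assumptions.** Two-sided alpha 0.05; normal approximation; effect δ in units of the residual SD; the same δ in both GWG arms; n = 150 analysed per arm unless stated.

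**1. Standard errors**

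- One GWG arm v PPWL-only: √(2/150) = 0.1155 SD.
- Both GWG arms combined v PPWL-only: √(1/300 + 1/150) = 0.1000 SD.
- Ratio: 1.155. The arm-by-arm standard error is 15.5% larger. With equal arms this ratio does not depend on n, alpha or δ. In variance terms, the combined contrast has 0.0100/0.01333 = 0.75 of the arm-by-arm variance.

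**2. Detectable effect at 80% power**, (1.960 + 0.842) × SE

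- 150 per arm: 0.323 SD arm-by-arm, 0.280 SD combined.
- If all 755 were randomized and analysed (755/3, so 251 per arm): 0.250 SD and 0.217 SD.

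**3. Power by choice of test, 150 per arm.** Two arm-by-arm statistics that share a control have correlation 0.5, so the joint probabilities come from a bivariate normal. The 2-df test has noncentrality n × δ² × 2/3, which is 10.47 at 0.323 SD and 7.85 at 0.280 SD.

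| Rule | δ = 0.323 SD | δ = 0.280 SD |
|---|---|---|
| One arm-by-arm test | 80% | 68% |
| Both arm-by-arm tests required | 69% | 53% |
| 2-df test of three means | 83% | 71% |
| Combined contrast | 90% | 80% |

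**4. Split results.** P(exactly one significant) = 2 × [P(one given test) − P(both)].

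- At 0.323 SD: 2 × (0.800 − 0.687) = 0.226, or 23% of trials.
- At 0.280 SD: 2 × (0.680 − 0.532) = 0.296, or 30% of trials.

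**5. False positives if either unadjusted test may be claimed.** With δ = 0, 1 − P(|Z₁| < 1.96 and |Z₂| < 1.96) at correlation 0.5 is 0.0907, so 9.1% within Hypothesis 1.

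**The case against.** The strongest reply is that the gap is narrower than it looks and that pooling is only one way to close it. The hypothesis and comparator are stated, and a 2-df test could not by itself establish a directional claim against a named control. Two arm-by-arm tests with a multiplicity rule would also remove the ambiguity. A Dunnett procedure that counts either arm as success has 86.0% power at 0.323 SD against 89.9% for the combined contrast, and 74.7% against 80.0% at 0.280 SD, so the gain over that competitor is about 4 to 5 points. Without adjustment, the either-arm rule has 0.800 + 0.800 − 0.687 = 0.913, about 91% power at 0.323 SD; its cost is the 9.1% error rate.

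The gain also rests on equal effects. Women are "oriented to the assigned treatment condition" at baseline, so those in GWG+PPWL know that postpartum support will follow, and behaviour or retention could differ. As an illustration, if one arm has 0.30 SD and the other half of that, combined power is 61% against 67% for Dunnett; if the other arm has no effect, it is 32% against 66%.

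Much of this stands as context. An adjusted arm-by-arm plan would be valid, and the combined contrast is not the best choice under strongly unequal effects. But the assigned prenatal treatment is identical, so equal effects are the natural working assumption, and even with unequal effects the contrast validly estimates the average effect of the GWG programme over the two arms. An either-arm success is also a weaker claim than the hypothesis, which names both arms. None of this supplies the missing contrast or success rule.

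**Conclusion.** The concern holds. Section 6.3 leaves the Hypothesis 1 test and its success rule undefined, and the design supports one combined contrast that is more precise than arm-by-arm comparison. The firmest figure is the 15.5% larger arm-by-arm standard error, which needs only equal arms and a common residual variance. With 150 per arm and the stated assumptions, the undefined choice moves power from 69% to 90% at 0.323 SD and from 53% to 80% at 0.280 SD, comparing the both-required rule with the combined contrast.

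The absolute powers are conditional. Section 3.6 has 450 women randomized, whereas sections 6.2 and 6.4 have 450 completing, so the number analysed at Week 36 could be below or above 150 per arm. That changes absolute power but not the relative precision. The change should be made; the omission does not invalidate the model, which can already deliver the required contrast.

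**What to change.** In section 6.3, keep the three-arm ANCOVA and add a sentence: the primary test of Hypothesis 1 is the single 1-df contrast (0.5, 0.5, −1) of GWG-only, GWG+PPWL and PPWL-only on GWG at the final prenatal visit, with its alpha and sidedness stated. Report each GWG arm against PPWL-only, and the difference between the two GWG arms with its confidence interval, as secondary or descriptive. That difference serves as the check on the equal-effects assumption.

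Leave the Hypothesis 2 contrasts unchanged on this ground: GWG+PPWL and PPWL-only are treated differently during pregnancy, and the same-treatment argument for the two GWG arms ends at birth.

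The cost is one sentence, with the same data and the same model. The small downside is that the primary result becomes an average over the two GWG arms, and its power advantage shrinks or reverses if their effects differ markedly.
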